#### ***11.4.4 Efficacy Variables***

The pharmacodynamic efficacy of three Ziltivekimab doses compared to placebo will be assessed by evaluating the following:

#### 11.4.4.1 Primary

- Difference in percent change in hs-CRP levels from Baseline (average of the hs-CRP value prior to randomization and Day 1) to Week 13 between each active group and placebo.

#### 11.4.4.2 Secondary

- Difference in change in SAA from Baseline to Week 13 between each active group and placebo.
- Difference in percent change in fibrinogen from Baseline to Week 13 between each active group and placebo.

#### 11.4.4.3 Exploratory

- Difference in percent change in hs-CRP levels from Baseline to End of Treatment (Weeks 23 through 24) between each active group and placebo.
- Difference in percent change in serum NT-pro-BNP from Baseline (average of the NT-pro-BNP value prior to randomization and Day 1) to Week 13 and to End of Treatment (Weeks 23 through 24) between each active group and placebo.
- Difference in change in SAA from Baseline to End of Treatment (Weeks 23 through 24) between each active group and placebo.
- Difference in percent change in fibrinogen from Baseline to End of Treatment (Week 24) between each active group and placebo.
- Difference in change in hemoglobin from Baseline (average of the two most recent hemoglobin values prior to randomization and Day 1) to Week 13 and to End of Treatment (Weeks 23 through 24) between each active group and placebo.
- Difference in change in serum albumin from Baseline (average of the two most recent serum albumin values prior to randomization and Day 1) to Week 13 and to End of Treatment (Weeks 23 through 24) between each active group and placebo.
- Proportion of patients achieving hs-CRP response at Week 13 and to End of Treatment (Weeks 23 through 24), defined as hs-CRP <2.0 mg/L in each active group and placebo.
- Difference in change in ST2 from Baseline to Week 13 and to End of Treatment (Week 24) between each active group and placebo.
- Difference in percent change in Lp(a) from Baseline to Week 13 and to End of Treatment (Weeks 23 through 24) between each active group and placebo.

- Difference in percent change in LDL-C, triglycerides, ApoB, ApoA1, ApoB/ApoA1, and lipid profile by NMR spectroscopy from Baseline to Week 13 and to End of Treatment (Weeks 23 through 24) between each active group and placebo.
- Difference in change of creatinine based eGFR and cystatin C-based eGFR from Baseline to Week 13 and to the End of Treatment (Weeks 23 through 24) between each active group and placebo.
- Difference in change of UACR from Baseline to Week 13 and to End of Treatment (Weeks 23 through 24) between each active group and placebo.
- Difference in change of the total fatigue score (PROMIS Fatigue 13a short form and selected items from the PROMIS Fatigue item bank) from Baseline to Week 13 and to End of Treatment (Weeks 23 through 24) between each active group and placebo.
- Difference in change of the PROMIS interest in sexual activity item from Baseline to Week 13 and to End of Treatment (Week 24) between each active group and placebo.
- Difference in change of the Corvidia ePRO items from Baseline to Week 12 and to End of Treatment (Weeks 23 through 24) between each active group and placebo.
- Difference in change of the PGIS index from Baseline to Week 12 and to End of Treatment (Week 24) between each active group and placebo.
- Descriptive analyses of the PGIC index at Weeks 5, 13 and End of Treatment (Week 24) in each active group and placebo.
- Difference in change of the Optum SF-36 v2® Health Survey physical component summary (PCS), mental component summary (MCS) and domain scores from baseline to Week 13 and to End of Treatment (Weeks 23 through 24) between each active group and placebo.
- Difference in change of the EQ-5D-5L index from Baseline to Week 12 and to End of Treatment (Week 24) between each active group and placebo.
- Evaluation of the psychometric properties of the PROMIS Fatigue 13a short form and selected items from the PROMIS Fatigue item bank and the Corvidia ePRO items in CKD patients – to be described in a PRO psychometric analysis plan.
- Descriptive analyses by dose and treatment may be conducted on samples stored for analysis of exploratory biomarkers, genomic and transcriptomic analysis.
- Difference in change in TSAT from Baseline to peak level, Week 13 and End of Treatment (Weeks 23 through 24), between each active group and placebo.

- Difference in change in CHr from Baseline to peak level, Week 13 and to End of Treatment (Week 24) between each active group and placebo.
- Difference in change in TIBC from Baseline to Week 13 and to End of Treatment (Weeks 23 through 24) between each active group and placebo.
- Difference in change in serum ferritin from Baseline to Week 13 and to End of Treatment (Weeks 23 through 24) between each active group and placebo.
- Difference in change in serum iron from Baseline to Week 13 and to End of Treatment (Weeks 23 through 24) between each active group and placebo.
- Difference in change in serum hepcidin from Baseline to Week 13 and to End of Treatment (Week 24) between each active group and placebo.
- Difference in percent change in serum NT-pro-BNP from Baseline to Week 13 and to End of Treatment (Weeks 23 through 24) between each active group and placebo in patients with baseline NT-pro-BNP > 250 pg/mL.
- Difference in change in hemoglobin from Baseline (average of the two most recent hemoglobin values prior to randomization and Day 1) to Week 13 and to End of Treatment (Weeks 23 through 24) between each active group and placebo in patients with baseline hemoglobin < 11 g/dL.
- Difference in change in serum albumin from Baseline (average of the two most recent serum albumin values prior to randomization and Day 1) to Week 13 and to End of Treatment (Weeks 23 through 24) between each active group and placebo in patients with baseline albumin < 4.0 g/dL.

For the above efficacy variables, the observed values, changes from baseline, or percent changes from baseline (as applicable) will be summarized by treatment group using descriptive statistics using ITT.

The PROMIS Fatigue 13a short form contains 13 items that assess symptoms and impacts of fatigue ([Appendix B](#)). The total score of the PROMIS Fatigue 13a short form and selected items from the PROMIS fatigue item bank will be calculated as a raw score based on the average of the items. The observed value and change from baseline in total fatigue score will be summarized by treatment at each visit.

The PROMIS Sexual Function and Satisfaction (PROMIS SexFS) is a customizable self-reported set of measures that include 79 items in 11 domains, for the purpose of this protocol we are only using 1 item: interest in sexual activity, lubrication, vaginal discomfort, erectile function, global satisfaction with sex life, orgasm, anal discomfort, therapeutic aids, sexual activities, interfering factors, and screener questions. The PROMIS evaluations are to be

done on subjects' device at the clinic PRIOR to dosing. The observed value and the change from baseline will be summarized by treatment at each visit.

The Optum SF-36 v2® Health Survey is perhaps the most widely used health-related quality of life (HRQoL) survey instrument in the world today (Hays 2001). It is comprised of 36 items that assess eight health concepts: physical functioning, role limitations caused by physical health problems, role limitations caused by emotional problems, social functioning, emotional well-being, energy/fatigue, pain, and general health perceptions ([Appendix C](#)). Physical and mental health summary scores are also derived from the eight Optum SF-36 scales. The PCS, MCS, and domain scores will only be analyzed descriptively. The observed value and change from baseline in total Optum SF-36 v2® Health Survey score will be summarized by treatment. The Optum evaluations are to be done on subjects' device at the clinic PRIOR to dosing.

The CARES Corvidia ePRO is a new PRO instrument under development ([Appendix D](#)). It consists of 19 symptom items, with a 24-hour recall, asking patients to report their worst level of that symptom in the past 24 hours on a numeric rating scale from 0 (no symptom) to 10 (symptom as bad as I can imagine).

Data will be collected at home on subject's personal device or one provided by Corvidia; the questionnaire will be answered daily for 7 days prior to dose (Screening Day -7 to Day -1 prior to Dose 1 (Visit 1), Dose 2 (Visit 4), Dose 4 (Visit 7), and the last 2 weeks after Dose 6 (Visit 23-24). For each item, weekly scores will be derived as the average of the 7 consecutive daily scores as follows:

Baseline = average of Day -7 to Day -1

Visit 4 = average of Day 22 to Day 28

Visit 7 = average of Day 78 to Day 84

If more than 4 daily scores out of the 7 days (>50%) within the weekly period are missing, then the score is set to missing.

A bi-weekly score (the End of Treatment) will also be derived as the average of Day 155 to Day 168. If more than 8 daily scores out of the 14 days (>50%) within the bi-weekly period are missing, then the score is set to missing.

Psychometric analyses will be conducted using the trial data to assess the psychometric properties of the CARES Corvidia ePRO instrument. The structural validity of CARES Corvidia ePRO instrument will be evaluated by means of exploratory factor analysis. A total summary scale or set of scales will be proposed in light of the factor loadings as well as clinical and conceptual considerations. Additional details will be described in the PAP. The score(s) developed as psychometrically sound will be used to evaluate efficacy.

Summary measures of compliance at each analysis visit will be derived among those patients who are expected to have PRO assessments. The completion rate will be defined as the total number of actual completed diary entries divided by the expected number of diary entries in a given time period (total number of days X number of expected patients).

The observed value and change from baseline on the developed scores will be summarized by treatment at each analysis visit.

The Patients' Global Impression of Change (PGIC) scale and the Patients' Global Impression of Severity (PGIS) scale represent clinically relevant tools to assess perceived impact of disease management. The PGIC evaluates overall health status as perceived by the patient in a seven-point, single-item scale ranging from 'very much worse' to 'no changes' to 'very much improved'. The PGIS is a 5-point scale (from no symptoms to very severe symptoms) and patients are asked to rate their overall severity of symptoms in the present (e.g., at each visit). The PGIC and PGIS are the most commonly used anchor based method of assessing clinically important change and severity in which the external judgment of meaningful change is made by the patient ([Appendix E](#)). The PGIC and PGIS evaluations will be done on subjects' device at the clinic PRIOR to dosing. Descriptive statistics (counts and percentages) for each response option at each scheduled visit for both PGIC and PGIS (separately) will be provided. A stacked column chart showing the distribution of responses at each scheduled visit will also be provided.

The EurQol-5D-5L (EQ-5D-5L) is a standardized measure of health status developed by the EuroQol Group in order to provide a simple, generic measure of health for clinical and economic appraisal ([Appendix F](#)). Applicable to a wide range of health conditions and treatments, it provides a simple descriptive profile and a single index value for health status that can be used in the clinical and economic evaluation of health care as well as in population health surveys. EQ-5D is designed for self-completion by respondents and is ideally suited for use in postal surveys, in clinics, and in face-to-face interviews. It is cognitively undemanding, taking only a few minutes to complete. Instructions to respondents are included in the questionnaire.

The EQ-5D-5L is to be done on a subject's device at the clinic PRIOR to dosing. EQ-5D-5L consists of two parts:

- EQ-5D-5L descriptive system
- Visual Analog Scale (VAS) with instant recall of "how you feel today"; scale goes from 0-100, where 100 means the best health you can imagine and 0, the worst one.

The EQ-5D-5L descriptive system includes the basic domains common to each generic health status measure: mobility, self-care, usual activities, pain/discomfort and

anxiety/depression. The instrument includes one single question per domain. For each question, there are 5 levels of responses, corresponding to increasing levels of impairment (no problems, slight problems, moderate problems, severe problems, and extreme problems), and coded 1 to 5.

Only descriptive analyses of the EQ-5D-5L results will be presented. Number and percentage of patients with each of five levels (no problems, slight problems, moderate problems, severe problems, and extreme problems) of response in each domain will be presented by treatment and visit. The observed value and change from baseline on the EQ-5D-5L VAS score will be summarized by treatment at each analysis visit.

Additional exploratory analyses of the PROs collected in the study will be described in the PROSAP.

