Statistical Methods Analysis	
The following analysis Populations are defined for the different types of data analysis:
 

• Intent-to-treat (ITT) analysis population: all patients randomized.

• Per-protocol (PP) analysis population: all patients randomized who completed the study and did not incur a significant protocol violation.

• Pharmacokinetics (PK) analysis population: all patients randomized and who received at least one dose of Test or Reference product and who had at least one post-dose PK blood sample.

• Safety analysis population: all patients randomized and who received at least one dose of Test or Reference product.

 
All study-collected data will be summarized by treatment group for the appropriate analysis population, using descriptive statistics, graphs, and/or raw data listings. Descriptive statistics for continuous variables will include number of patients (n), mean, standard deviation (SD), median, quartiles (Q1 and Q3), minimum (min) and

	
maximum (max) values for the observed value and change from baseline will be reported. Analysis of categorical variables will include frequency and percentage.
 
For efficacy variables, the difference between each active group and placebo will be presented. A mixed model for repeated measures (MMRM) will be used for this purpose, with baseline hemoglobin (<math>\geq 11</math> or <math>< 11</math> g/dL), CKD stage (3, 4 or 5), treatment groups, visit and treatment group-by-visit interaction as categorical fixed effects, baseline value and baseline-by-visit interaction will be included as covariates. The least square means for each dose, the least square mean differences from placebo along with the associated 95% confidence intervals (CIs) and p-values will be presented. If the normality assumption is not met, a nonparametric test will be selected for efficacy analysis.

Study Centers	Approximately 50-60 study sites
Sponsor	Corvidia Therapeutics Inc.

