#### **3.1.3.2 Secondary**

All secondary and exploratory analyses will be performed with the Intent-to-Treat (ITT) population.

- Difference in change in SAA from Baseline to Week 13 between each active group and placebo.
- Difference in percent change in fibrinogen from Baseline to Week 13 between each active group and placebo.

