### 11.1 Sample Size

The primary efficacy endpoint is percent change from baseline in hs-CRP (average of the hs-CRP value prior to randomization and Day 1) to Week 13 between each active group and placebo. Based on the observed treatment difference in percent change from baseline in hs-CRP of -60.74% between combined COR-001-01 active groups and placebo and the associated pooled SD of 16.893% in hs-CRP at Week 4 from the final analysis of study COR-001-SC1, a sample size of 54 per group yields more than 99% power with 2-sided alpha=0.05. Taking into consideration the dropout rate of 10% by the end of the study, a sample size of 60 per group is planned for this study

Approximately 240 patients (60 per group) will be randomized.

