#### 11.3.2 Analysis Populations

**Intent-to-Treat (ITT) analysis population:** all patients randomized.

The ITT analysis populations will be the primary population for the analyses of disposition and baseline data and efficacy endpoints.

**Per-Protocol analysis population:** all patients randomized who completed the study and did not incur a significant protocol violation

For the ITT analysis populations and per-protocol populations, treatment classification will be based on the randomized treatment.

**Pharmacokinetics (PK) analysis population:** all patients randomized and who received at least one dose of Test or Reference product and who had at least one post-dose PK blood sample

**Safety analysis population:** all patients randomized and who received at least one dose of Test or Reference product.

For the PK analysis population and safety population, treatment classification will be based on the treatment actually received.

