### **11.3.4 Missing Data Handling**

Unless otherwise specified, missing data will not be imputed and the analyses will be based on observed data only.

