#### ***11.4.3 Efficacy Analysis***

For all efficacy variables, the number of patients (n), mean, standard deviation (SD), median, quartiles (Q1 and Q3), minimum (min) and maximum (max) values for the observed value, change from baseline, or percent change from baseline (as applicable) will be reported. The difference (Ziltivekimab - Placebo) in changes or percent changes (as applicable) will be presented.

A mixed model for repeated measures (MMRM) will be used to evaluate change or percent change from baseline. The model will include variables for baseline hemoglobin ( $\geq 11$  or  $< 11$  g/dL), CKD Stage (3, 4 or 5), treatment group, visit and treatment group-by-visit interaction as categorical fixed effects, baseline value and baseline-by-visit interaction will be included as covariates. The least squares means for each dose, the least squares mean differences from placebo along with the associated 95% confidence intervals (CIs) and p-values will be presented. If the normality assumption is not met, a nonparametric test will be selected for efficacy analysis. Details of normality test and nonparametric test will be provided in the Statistical Analysis Plan.

An unstructured covariance matrix will be used to model the within-subject correlation. The Kenward-Roger approximation will be used to adjust the denominator degrees of freedom. The analysis will be performed based on all observed post-baseline scores without any imputation of missing data. In the case when the MMRM fails to converge using an unstructured covariance matrix in any stage, a less stringent covariance matrix (e.g., autoregressive 1) will be used.

Sensitivity analyses will be conducted to explore the robustness of the result for primary efficacy endpoint based on MMRM. Full details will be pre-specified in SAP and documented prior to database lock of the study.

The differences in proportions and 95% CIs will be based on the normal approximation to binomials.

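### The normal-approximation 95% CI fixed for differences in proportions under-covers for the hs-CRP <2.0 mg/L responder endpoint if response is rare on placebo and near-universal on active drug (minor)

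*Protocol*

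**What the plan says.** Section 11.4.4.3 lists the responder endpoint among the exploratory variables: "Proportion of patients achieving hs-CRP response at Week 13 and to End of Treatment (Weeks 23 through 24), defined as hs-CRP <2.0 mg/L". The proportion is to be given for every arm. Section 11.4.3 sets the method for proportions in one sentence: "The differences in proportions and 95% CIs will be based on the normal approximation to binomials". That section sends the normality check, the nonparametric alternative and the primary-endpoint sensitivity analyses to the SAP, but not the interval for proportions.

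On the population, Section 3.1.3.2 states: "All secondary and exploratory analyses will be performed with the Intent-to-Treat (ITT) population". The synopsis defines this set: "Intent-to-treat (ITT) analysis population: all patients randomized". Section 11.3.4 gives the missing-data default: "Unless otherwise specified, missing data will not be imputed and the analyses will be based on observed data only". No section gives a denominator or a missing-data rule specific to the responder endpoint. Section 11.4.4.4 limits multiplicity control to the primary endpoint.

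**The concern.** The Wald interval for a difference in proportions is weakest when one rate is near 0 and the other near 1. That pattern is plausible here. Entry requires hs-CRP of at least 2.0 mg/L (Section 4.1), so few placebo patients may fall below the threshold, and the sample-size section assumes a large hs-CRP reduction on active drug. In such data the estimated variance is small and the symmetric interval tends to be too short, so the stated 95% overstates the certainty of the dose-placebo contrast. The threshold matters to the sponsor: Section 3.5.4 names hs-CRP below 2 mg/L as a secondary goal of the dosing.

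A second, smaller issue is what the percentage means. The MMRM uses a patient's other visits when one value is missing; a single-visit proportion does not. Under the observed-data default, a patient without a value at the visit belongs to the ITT population but not to the denominator.

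**Working it through.** **Inputs.** From Section 11.1: 54 evaluable per group, difference 60.74 points, SD 16.893, 10% dropout by the end of the study, 60 randomized per group. Responder rates are assumptions, because the protocol states none; the range is shown.

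**The plan's own figure.** Section 11.1 says "a sample size of 54 per group yields more than 99% power with 2-sided alpha=0.05". The noncentrality is 60.74 / (16.893 × √(2/54)) = 18.68, so power is above 0.9999, and 54 / (1 − 0.10) = 60. The figure reproduces. It concerns the primary endpoint and says nothing about the responder rate.

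**Exact coverage.** The planned interval is (p̂₁ − p̂₂) ± 1.96 × √[p̂₁(1 − p̂₁)/n + p̂₂(1 − p̂₂)/n]. For true rates p₁ and p₂, coverage is the sum of Bin(x₁; n, p₁) × Bin(x₂; n, p₂) over all pairs (x₁, x₂) whose interval contains p₁ − p₂. The Newcombe interval, built from the two Wilson intervals, is evaluated the same way.

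| Active vs placebo (assumed) | Wald, n = 54 | Newcombe, n = 54 | Wald, n = 60 | Newcombe, n = 60 |
|---|---|---|---|---|
| 0.50 vs 0.10 | 94.5% | 95.0% | 94.8% | 95.0% |
| 0.80 vs 0.10 | 93.0% | 93.9% | 94.2% | 95.5% |
| 0.90 vs 0.10 | 91.3% | 94.6% | 94.3% | 94.1% |
| 0.95 vs 0.05 | 90.3% | 95.2% | 93.5% | 95.9% |

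Over a grid of active rates 0.50 to 0.95 and placebo rates 0.05 to 0.30, with n = 54, Wald coverage averages 93.7% (range 90.3% to 94.9%) and Newcombe 94.9% (93.0% to 95.6%). With n = 60, Wald averages 94.1% with a minimum of 93.0%; Newcombe averages 94.9% with a minimum of 94.1%.

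The gap between n = 54 and n = 60 is partly due to discreteness. At 0.90 vs 0.10 the same sum gives 95.0% for n = 53 and 91.3% for n = 54. The number of patients with a value will not be known in advance, so the better figures cannot be relied on.

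**Expected width at n = 54, Wald against Newcombe.** 0.308 against 0.306 (0.50 vs 0.10); 0.263 against 0.264 (0.80 vs 0.10); 0.222 against 0.229 (0.90 vs 0.10); 0.159 against 0.178 (0.95 vs 0.05).

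**Denominator.** Suppose 6 of 60 are missing in each arm, with 43 active and 5 placebo responders observed.
- Observed data: 43/54 − 5/54 = 70.4 points.
- Missing counted as non-response: 43/60 − 5/60 = 63.3 points.
- Extremes over all possible missing outcomes: 43/60 − 11/60 = 53.3 points and 49/60 − 5/60 = 73.3 points.

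**Effect of dropout on width.** At fixed proportions the Wald width scales with 1/√n, so going from 60 to 54 multiplies it by √(60/54) = 1.054. The interval becomes 5.4% wider.

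**The case against.** The extreme rates are assumptions, and at moderate rates the Wald interval does nearly as well as any other. With 60 per arm the shortfall in the tabulated cases is at most 1.5 points. Newcombe is not better everywhere: at 0.90 vs 0.10 with n = 60 it covers 94.1% against 94.3%. The endpoint is exploratory, and Section 2 bases the dose choice on hs-CRP reduction, lipids, neutrophils and platelets, not on a responder rate. All of this stands, and it sets the severity. It does not rescue the interval, which is a method the protocol has chosen and which is the weaker of the two on average.

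A reader might infer that dropout makes the interval too narrow. It does not: at fixed proportions fewer patients widen it. Compared with counting missing as non-response, the direction depends on the rates: observed-data width 0.308 against 0.288 with 27 and 5 responders, but 0.228 against 0.246 with 48 and 5.

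A reader might also infer that the observed-data rate is biased and non-responder counting corrects it. The documents do not support that. If the true rates are 80% and 10% and missingness is unrelated to response, observed data return the true 70 points, while non-responder counting at 10% dropout returns 0.9 × 70 = 63. Section 4.6 describes a long pharmacodynamic effect, and Section 3.5.4.1 gives mean half-lives of 48 to 56 days in CKD patients, so some who stop may remain below 2.0 mg/L. The opposite bias arises if patients with missing values respond less often. The loss is also limited: 10% is by study end, so Week 13 loss is probably smaller, and Section 5.6 asks for Week 24 procedures at early termination, which may supply End of Treatment values though not a missing Week 13 value. Finally, the missing-data default opens with an exception clause, so the SAP may set a rule for this endpoint.

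**Conclusion.** The point holds as a minor one. The interval prescribed in Section 11.4.3 under-covers when placebo response is near 0 and active response near 1. At n = 54 the shortfall from 95% is 2.0 points at 0.80 vs 0.10, 3.7 at 0.90 vs 0.10 and 4.7 at 0.95 vs 0.05. At n = 60 the same cases fall short by 0.8, 0.7 and 1.5 points. At moderate rates the shortfall is about half a point. These sizes rest on assumed responder rates and on equal numbers with a value in each arm.

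The denominator is a matter of clarity and not a demonstrated bias: the observed-data percentage describes patients with a value at the visit, and the ITT label suggests more. The primary analysis, the sample size and the multiplicity procedure are unaffected.

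**What to change.** In Section 11.4.3, replace the normal approximation for differences in proportions by a named score interval, Newcombe or Miettinen-Nurminen. The coverage figures above are for Newcombe. The cost is one sentence and, at extreme rates, a slightly wider interval (0.178 instead of 0.159 at 0.95 vs 0.05, n = 54); at 0.80 vs 0.10 the widths are practically equal.

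For the responder endpoint, state in the protocol or SAP that the observed-data rate is among patients with a value at the visit. Add a supportive rate over all randomized patients with missing counted as non-response, and report the number missing per arm at each time point. Present the two side by side without calling either the unbiased one. This costs one extra table row per time point and no new data.

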#### **5.3.7                   *Visits 6 through 9, Weeks 9 through 21***

- Concomitant and Prior Medications (not Week 12)
- Vital Signs (not Week 12)
- BMI (Week 13 only)

- Hematology (not Week 12)
- Lipids (fasting 8 hours; Week 13 only)
- Chemistry (not Week 12)
- Spot urine protein-creatinine ratio (Week 13 only)
- Urinalysis (including albumin) (Week 13 only)
- Iron Indices (Week 13 only)
- Serum hepcidin (Week 13 only)
- Special RBCs (Week 13 only)
- IL-6 (pre-dose) (not Week 12)
- hs-CRP (not Week 12)
- Ziltivekimab trough PK (not Week 12)
- ADA (pre-dose) (not Week 12)
- CKD Biomarkers (Week 13 only)
- NT-pro-BNP (Week 13 only)
- Lp(a), ApoB, ApoA1 (fasting 8 hours; Weeks 9 and 13 only)
- Lipid profile by NMR spectroscopy (fasting 8 hours; Week 13 only)
- Cardiac Risk Biomarkers: SSA, fibrinogen and ST2 (Week 13 only)
- Storage samples for Exploratory Biomarkers and RNA Testing (Week 13 only)
- Coagulation (INR): Patients on warfarin only (not Week 12)
- Adverse Events (not Week 12)
- PROMIS® 13a and Fatigue Items (Week 13 only)
- PROMIS® Sexual Interest Items (Week 13 only)
- CARES Corvidia ePRO (Week 12 only)
- PGIS (Week 12 only)
- PGIC (Week 13 only)
- EQ-5D-5L (Week 13 only)
- Optum SF-36 v2 (Week 13 only)

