**15.2                    Appendix B    PROMIS® (Patient-Reported Outcomes Measurement Information System)**

## PROMIS Items

	During the past 7 days.....	Not at all	A little bit	Somewhat	Quite a bit	Very much
I feel fatigued	1  2  3  4  5 					
I feel weak all over	1  2  3  4  5 					
I feel listless ("washed out")	1  2  3  4  5 					
I feel tired	1  2  3  4  5 					
I have trouble starting things because I am tired	1  2  3  4  5 					
I have trouble finishing things because I am tired	1  2  3  4  5 					
I have energy	1  2  3  4  5 					
I am able to do my usual activities	1  2  3  4  5 					
I need to sleep during the day	1  2  3  4  5 					
I am too tired to eat	1  2  3  4  5 					
I need help doing my usual activities	1  2  3  4  5 					
I am frustrated by being too tired to do the things I want to do	1  2  3  4  5 					
I have to limit my social activity because I am tired	1  2  3  4  5 					

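### Three stated rules for exploratory patient-reported endpoints contradict themselves or fail as written: the CARES missing-day limit, the EQ-5D-5L week, and the unreversed average of the fatigue items

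*Protocol*

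**What the plan says.** **CARES.** Protocol 11.4.4.3 averages the daily item scores over a 7-day window, or a 14-day window at End of Treatment. The weekly score is set to missing under this condition: "If more than 4 daily scores out of the 7 days (>50%) within the weekly period are missing". The two-week score has the matching condition: "If more than 8 daily scores out of the 14 days (>50%) within the bi-weekly period are missing".

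**EQ-5D-5L.** The exploratory endpoint is worded "Difference in change of the EQ-5D-5L index from Baseline to Week 12" and to Week 24. The same week appears in the Synopsis and in 3.1.3.3. The visit list in 5.3.7, covering Weeks 9 to 21, has "EQ-5D-5L (Week 13 only". Section 11.4.4.3 and the Table 2 footnote place the questionnaire in the clinic before dosing.

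**Fatigue.** Section 11.4.4.3 states "The PROMIS Fatigue 13a short form contains 13 items that assess symptoms and impacts of fatigue". The total score, which also takes in selected item-bank items, "will be calculated as a raw score based on the average of the items". Appendix B prints those 13 items and three item-bank fatigue items, all coded 1 (not at all) to 5 (very much). Most are worded like "I feel fatigued". Two are worded the other way: the item on having energy, and "I am able to do my usual activities".

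**The concern.** Each of these is a rule that the protocol states, not a detail it leaves open.

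- **CARES.** A count and a percentage are given for the same cut-off and they part company at one value in each window. Two programmers could follow the same sentence and produce different datasets. CARES is a new instrument whose resulting scores are meant to evaluate efficacy, so its derivation should have one reading.
- **EQ-5D-5L.** An endpoint is named at a week when the instrument is not given.
- **Fatigue.** If the two positively worded items enter the mean as coded, an improving patient moves up on them and down on the other 14, and the changes partly cancel. The change in total fatigue score between each active group and placebo is a listed endpoint, so its raw size would be understated and its scale would not have the natural 1-to-5 range.

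**Working it through.** **1. CARES missing days** (inputs: the counts and percentage in 11.4.4.3)

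Proportion missing = m/7 or m/14.

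| Window | Days missing | Proportion | By the >50% label | By the count |
|---|---|---|---|---|
| 7 days | 3 | 42.9% | kept | kept |
| 7 days | 4 | 57.1% | missing | **kept** |
| 7 days | 5 | 71.4% | missing | missing |
| 14 days | 7 | 50.0% | kept | kept |
| 14 days | 8 | 57.1% | missing | **kept** |
| 14 days | 9 | 64.3% | missing | missing |

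Count and label disagree at exactly 4 of 7 and exactly 8 of 14. At those values a score resting on 3 of 7 or 6 of 14 days is kept by one half of the sentence and discarded by the other.

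**2. EQ-5D-5L week** (passages set side by side)

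- The endpoint lists (Synopsis, 3.1.3.3, 11.4.4.3) name Week 12.
- Section 5.3.7 names Week 13 as the only EQ-5D-5L assessment in Weeks 9 to 21. In the same list, CARES and PGIS are the items given at Week 12.
- Section 11.4.4.3 and the Table 2 footnote require clinic completion before dosing. Week 12 has no visit number in Table 2, is marked as having no visit in the CARES footnote, and has no dosing (5.3.8).

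No Week 12 value is therefore collected. The Table 2 row for EQ-5D-5L is not legible in the text read from the PDF, so this rests on the prose and footnotes.

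**3. Fatigue score** (inputs: the scoring sentence in 11.4.4.3 and the items in Appendix B)

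Items: 13 + 3 = 16, of which 14 are worded as fatigue and 2 as its absence. Codes are taken as 1 to 5 in the same order for all.

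Unreversed 16-item mean:
- no fatigue: (14×1 + 2×5)/16 = 1.50, instead of 1
- worst fatigue: (14×5 + 2×1)/16 = 4.50, instead of 5
- 1-point improvement on every item: (−14 + 2)/16 = −0.75, instead of −1.00

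On the 13-item form alone (11 and 2), the last line becomes (−11 + 2)/13 = −0.69.

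The spread of the score shrinks as well, so the raw loss overstates the loss of signal. Assume 16 items of equal variance with a common inter-item correlation ρ after alignment. The variance of the item sum is proportional to 16 + 240ρ when the two items are reversed and 16 + 128ρ when they are not. The standardised effect that remains is

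0.75 / √[(16 + 128ρ)/(16 + 240ρ)]

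| ρ (assumed) | Share of standardised effect kept |
|---|---|
| 0.1 | 0.88 |
| 0.3 | 0.95 |
| 0.6 | 0.985 |
| 0.8 | 0.99 |

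**The case against.** The best counter-case is on the fatigue score. A raw score may mean only that it is not converted to a T-score. Item-level scoring of an established instrument often sits in an analysis plan, and response codes on a form are not a scoring algorithm. The table in Appendix B is also damaged in the text read from the PDF, so the uniform coding needs checking against the original. Much of this stands: the protocol is silent on reversal and does not forbid it. But it does state a rule, and a plain reading of that rule averages the printed codes.

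A reader might infer that a quarter to a third of the fatigue effect, or of the power to see it, is lost. The documents do not support that. The 25% and 31% losses are in raw units, assume equal change on every item, and ignore the smaller SD. Nor do they show that the psychometric work on the fatigue items is harmed, since that follows a separate plan.

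On CARES, the count can be programmed as it stands, and every score it drops is indeed more than 50% missing. That is fair, and the protocol does not say whether the count or the percentage is the intended limit. A reader might also infer that sparse scores contaminate the CARES factor analysis. Section 11.4.4.3 does not say that the factor analysis uses these weekly averages, so no such effect is claimed.

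On EQ-5D-5L, the intended value is fairly evident. Week 13 is the only assessment in that stretch, its window (Days 85–91) adjoins Week 12 (Days 78–84), and the section promises only descriptive EQ-5D-5L results. The information is not lost; the label is wrong, in all three endpoint lists.

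**Conclusion.** The point holds in all three parts, as corrections to stated rules for exploratory endpoints.

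- **CARES:** a definite internal contradiction, confined to one count in each window (4 of 7 and 8 of 14, both 57.1% missing).
- **EQ-5D-5L:** the change to Week 12 cannot be computed as worded. Week 13 data will exist, so the cure is to change the label.
- **Fatigue:** the rule as written averages items of opposite direction. If the two items are left unreversed, the 16-item score spans 1.5 to 4.5 and a uniform 1-point change shows as 0.75 (0.69 on 13 items). The standardised loss on the 16-item score is about 1% to 5% for ρ of 0.3 or more, and about 12% at 0.1. This rests on the printed coding being as read, equal change on all items, equal item variances and an assumed correlation.

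The primary and secondary endpoints, the sample size and the multiplicity procedure are not affected.

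**What to change.** 1. **CARES:** make count and percentage agree. The simplest wording sets the score to missing when 4 or more of 7, or 8 or more of 14, daily scores are missing. If the present counts are intended, correct the percentage instead. Cost of the first option: a few more scores become missing.
2. **EQ-5D-5L:** change Week 12 to Week 13 in the Synopsis, 3.1.3.3 and 11.4.4.3. Leave Week 12 in place for CARES and PGIS, where it matches the visit list. Cost: none beyond the edit.
3. **Fatigue:** check the coding in the original Appendix B. If it is uniform, state that the energy item and the usual-activities item are recoded as 6 minus the response before averaging. Cost: one sentence and one line of code.

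None of these needs new data or adds burden for patients or sites.
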